10.5 Missing Data

Missing data are very common in drug abuse research, with the amount of missingness increasing as the length of follow-up increases. The maximum likelihood methodology that will be employed for the estimation in the hierarchical model allows observations with arbitrary pattern of missingness to be used in estimation. However, unbiasedness of the resulting estimates is only guaranteed when the observations are missing completely at random. When observations are not missing completely at random, pattern mixture models (Little and Rubin, 1987) can be used to compare the outcomes across the various patterns of missing data. In pattern mixture analysis, participants are grouped according to their missingness pattern and such grouping identifies an indicator variable that can then be used in the analysis. The impact of the treatment arm on the missingness pattern is of greatest importance. However, such analysis can be confounded when participants in a particular missingness pattern group belong to one treatment arm only. This is especially likely to happen when there are multiple visits and therefore potentially many missingness patterns.

10.6 Sample Size and Power Calculations

[figure not shown]
The sample size required for detecting a time by group interaction is estimated using the formulas due to Hedeker et al. (Hedeker, Gibbons, Waternaux, 1999). The following assumptions are employed. Four replicate, continuous, approximately normally distributed outcome (Percent of Days of Drug Use) measurements are to be obtained at 4, 8, 13 and 26 weeks (the baseline value is to be entered as a covariate). A two-sided type-I error rate (alpha) is set at 0.05 and power (1-beta) is assumed as 80%.

The expected effect size was determined by incorporating information from two sources. First, in the Brown, Serganian, et al. (2002) study of group-based TSF versus an active comparison therapy (relapse prevention [RP]), the standard deviation for "days of use in previous 90 days" was 24 days in the TSF group and 17.7 days in the RP group, giving a pooled estimate of the standard deviation of 21.3 days, or 23.7% of days of substance use over the 6-month assessment window. Second, clinicians and program directors from multiple CTPs in the CTN were asked about what they viewed as a potentially clinically meaningful difference between their TAU and an experimental treatment such as TSF. They indicated that a 10% difference, on average, in percent days of use between TAU and a new therapy would be clinically meaningful. A 10% difference divided by a standard deviation of 23.7% gives a standardized effect size of 10/23.7 = 0.42. Effects of this magnitude are in the 'small' to 'medium' range in the power analysis literature (Cohen, 1983). Based on or anticipated ability to track, follow, and assess participants at the follow-up points, a total retention rate of 70% for the duration of the trial was assumed, with the dropout rate occurring evenly over the 4 post baseline points is assumed; however, it should be noted that the follow-up rates in the Brown, Serganian, et al. (2002) was only about 50% at the 6-month follow-up. Compound symmetry with a correlation parameter of 0.5 is also assumed; however, there is no information available on the correlation pattern between observations.

Given this, we looked at a range of potential sample sizes based upon these initial assumptions, as well as additional assumptions in which the attrition rates and correlation parameters varied from the original assumptions. The table below shows potential sample sizes for effect size of 0.4, with attrition rates of either 30% or 50%, and the correlation parameters (rho) ranging from 0.3 to 0.7.

Effect Size	Attrition Rate	rho	Sample Size/Condition
0.4	0.3	0.3	139
0.4	0.3	0.5	165
0.4	0.3	0.7	191
0.4	0.5	0.3	181
0.4	0.5	0.5	213
0.4	0.5	0.7	245

Similarly, the graph below presents potential sample sizes and levels of power based on an effect size of 0.42 with differing levels of rho.

Ref: Hedeker, Gibbons, Waternaux, J. Ed. Beh. Stat, 199, 24 (1), 70-93

Based on these projections, we propose equal sample sizes of approximately 200 in each of two arms (TAU and STAGE-12). Based on the above table, this would provide power of 80%, rho of 0.5, both more originally assumed, while accommodating a potentially higher attrition rate than used in the original assumptions. And, based on the graph above, using the effect size of 0.42, rho = .5, and an attrition rate of 30%, this would provide power of approximately 85%. Thus, the trial is adequately powered to detect a small to moderate change in the difference in the change over time between the two groups in average level of drug use. As described below, a blinded variance check of the primary endpoint will be conducted relatively early in the trial to allow a more accurate estimate of this parameter to determine the adequacy of the projected sample size.

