10.3 Primary Outcomes

10.3.1 Hierarchical linear model

The primary outcome variable will be percent of days of stimulant use over the assessment window, based on Substance Use Calendar alone and assessed at baseline, weeks 4 and 8/end of treatment, 3 months and 6 months. This measure will be analyzed using hierarchical linear models. Specifically, the trajectory over time for an individual patient will be described by the Level-1 model

(1)
$$Y_{ijk} = X_i \varphi + \beta_{0ij} + \beta_{ij} t_{ik} + \varepsilon_{ijk}, \qquad k=1,..., n_i$$

where Y_{ijk} and ε_{ijk} are percent of days of stimulant use and error term of participant i at site j at post-baseline assessment k, β_{0ij} is the baseline percent of stimulant use, β_{ij} is the slope for participant i, t_{ik} is the number of weeks at post-baseline assessment k, n_i is the number of post-baseline assessments for participant i, which can differ between the participants reflecting attrition; X_i is a baseline variable describing whether participant i was court mandated for treatment ($X_i = 1$) vs. not court-mandated for treatment ($X_i = 0$).

The Level-2 model describes the slope for participant *i* as a function of the treatment arm:

(2)
$$\beta_{ii} = \alpha_{0i} + \alpha_1 I(STAGE-12) + b_{ii}$$

Here α_{0j} is the intercept for participants at the *j*th treatment site, α_1 is the effect of the STAGE-12 treatment, *I*(STAGE-12) is a 0-1 STAGE-12 treatment indicator and b_{ij} is a subject-specific random error term.

The Level-2 model also describes the baseline outcome measure for participant i:

$$\beta_{0ij} = \alpha_{00j} + b_{0ij}$$

Here α_{00j} is the intercept for participants at the *j*th treatment site and b_{0ij} is a subject-specific random error term.

The assumptions of the model are: a) $\mathbf{e}_{ij} = (\varepsilon_{ij1},...,\varepsilon_{ijn_i})^T$ are independent $N(0,\Sigma_i)$ where Σ_i depends in i only through its dimension, b) b_{ij} are independent $N(0, \sigma_b^2)$, uncorrelated with ε_{ijk} , c) b_{0ij} are independent $N(0, \sigma_0^2)$, uncorrelated with b_{ii} and ε_{ijk}

The primary analysis will evaluate the hypotheses H_0 : $\alpha_1 = 0$ vs. H_1 : $\alpha_1 \neq 0$ and rejection of the null hypothesis with $\alpha_1 < 0$ would indicate that STAGE-12 treatment reduces percent of days of substance use compared to TAU.

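### Section 10.6 states about 85% power where its own table implies about 90%, and the table does not behave like the slope test that is primary

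*Protocol*

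**What the plan says.** Protocol 10.6 names the test being sized: "The sample size required for detecting a time by group interaction is estimated using the formulas due to Hedeker et al". The outcome "measurements are to be obtained at 4, 8, 13 and 26 weeks (the baseline value is to be entered as a covariate"). The error rate and target are given as "A two-sided type-I error rate (alpha) is set at 0.05 and power (1-beta) is assumed as 80" percent. On covariance it says "Compound symmetry with a correlation parameter of 0.5 is also assumed", and it adds that nothing is known about the actual correlation pattern. Total attrition is 30%, spread evenly over the four post-baseline visits.

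The effect size is a 10-point difference divided by an SD of 23.7 points, which is 0.42. The table uses 0.4 and gives, per arm for rho 0.3/0.5/0.7:
- 30% attrition: 139/165/191
- 50% attrition: 181/213/245

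Two power statements follow for about 200 per arm. From the table, "this would provide power of 80%, rho of 0.5, both more originally assumed", with room for a higher attrition rate that is not named. From a graph, "using the effect size of 0.42, rho = .5, and an attrition rate of 30%, this would provide power of approximately 85" percent.

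Protocol 10.3.1 defines the primary test. "The Level-2 model describes the slope for participant *i* as a function of the treatment arm"; the hypothesis concerns the treatment coefficient alpha_1 in that slope. The intercept has no treatment term, and each participant has a random slope.

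**The concern.** The 85% and the row with 165 per arm share the same rho and attrition, so one can be derived from the other, and they disagree.

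The table also moves in an unexpected direction. Under compound symmetry, higher correlation usually makes a difference in slopes easier to detect, yet here the required number grows with rho. That suggests the table may have been computed for a contrast other than alpha_1.

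At stake is the section's conclusion that the trial is adequately powered. It rests on figures that do not agree with each other and are not shown to belong to the primary test. The overall sample size may be adjusted after the blinded variance check (5.2, 10.7), and 10.6 is the only calculation the protocol states for judging adequacy.

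**Working it through.** **Inputs, all from 10.6:** two-sided alpha 0.05 and 80% power, so z values 1.960 + 0.842 = 2.802; effects 0.42 and 0.4; visits at weeks 4, 8, 13 and 26; compound symmetry; 200 per arm; the six table rows.

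**Step 1. Effect size.** 10/23.7 = 0.42. This reproduces.

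**Step 2. Power implied by the table.** If a row needs N0 per arm for 80% power at effect 0.4, then power at n per arm and effect d is Phi[2.802 × sqrt(n/N0) × (d/0.4) − 1.960].

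| Row | N0 | d | Power at 200 per arm |
|---|---|---|---|
| 30%, rho 0.5 | 165 | 0.42 | 90.0% |
| 30%, rho 0.5 | 165 | 0.40 | 87.0% |
| 30%, rho 0.7 | 191 | 0.42 | 85.3% |
| 50%, rho 0.5 | 213 | 0.40 | 77.5% |
| 50%, rho 0.5 | 213 | 0.42 | 81.3% |

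The first line has the inputs of the 85% statement and misses it by 5 points. Equivalently, 165 × (0.4/0.42)² = 149.7 per arm would give 80% at 0.42, and about 171 would already give 85%.

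**Step 3. Required number for alpha_1.** In 10.3.1 both arms share an intercept. With equal arms, the variance of the estimated alpha_1 is 2/(nJ), where J is the sum over dropout patterns of p × t′V⁻¹t. Here p is the share of an arm with that pattern, t the weeks observed, and V the compound-symmetry matrix with unit variance. The assumptions are mine:
- the four post-baseline visits only;
- even dropout, so retention is 92.5/85/77.5/70% at 30% attrition;
- no random slope;
- a difference growing linearly from zero to 0.4 SD at week 26, so alpha_1 = 0.4/26 per week in absolute size.

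Then N = 2 × 2.802²/[(0.4/26)² × J]. At rho 0.5 and 30% attrition J is 586.6 and N = 113.

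| Attrition | rho 0.3 | rho 0.5 | rho 0.7 |
|---|---|---|---|
| 30%, protocol table | 139 | 165 | 191 |
| 30%, alpha_1 | 124 | 113 | 82 |
| 50%, protocol table | 181 | 213 | 245 |
| 50%, alpha_1 | 165 | 151 | 110 |

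The directions are opposite. If nobody is lost before week 4, the 30% line is 122/112/81. If baseline is modelled as a fifth outcome, it is 112/93/61. Both still fall.

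**Step 4. Dependence on the effect's time course.** At 200 per arm, effect 0.42, rho 0.5 and 30% attrition, the standard error of alpha_1 is sqrt[2/(200 × 586.6)] = 0.00413.
- Ramp to 0.42 at week 26: alpha_1 = 0.42/26 = 0.01615, ratio 3.91, power Phi(1.95) = 97.5%.
- Constant gap of 0.42 at all four visits: the model fits a slope reaching only 0.300 at week 26, so alpha_1 = 0.01154, ratio 2.79, power Phi(0.83) = 80%.

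A random-slope variance would lower both; 10.6 gives no value for it.

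**The case against.** Several objections have force.

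**Rising with rho is not impossible.** A reader might infer that a time-by-group interaction can never need more patients as rho rises. That is false. Variance is proportional to 1 − rho only for contrasts whose weights sum to zero within a person. The shared-intercept test also uses between-person information: in Step 3 its N rises from 98 at rho 0 to 124 at rho 0.3 before it falls. A non-centred contrast found by search gives 140/167/195 and 179/210/241, within 2% of all six rows. It was found by trial, so it does not prove how the table was made. What stands is narrower: over rho 0.3 to 0.7 the table does not follow the alpha_1 test under the assumptions given.

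**The graph is not available here.** The 85% is attributed to a graph that could not be checked. The text and the table still conflict, but the documents do not settle which is wrong.

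**The attrition sentence does not promise 50%.** It claims only a potentially higher rate. Linear interpolation between 165 and 213 puts 200 at about 45% attrition, and at effect 0.42 the 50% row is met (81%). The sentence is not shown to be false; it is unclear because it names no rate.

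**Compound symmetry is a planning simplification.** It is openly described as lacking data. The ramp and constant-gap shapes are my illustrations, and 10.6 does not say whether its average difference is across patients or across visits.

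**Conclusion.** Wrong as written, on two counts. The stated 85% contradicts the table row with the same rho and attrition, which implies 90.0%; this needs only the printed figures and the normal approximation. Section 10.6 is also not shown to give the power of alpha_1, because its table rises where that test's N falls, and the effect's time course and the random-slope variance are left out. The second count rests on the assumptions listed in the working.

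A reader might infer that the trial is underpowered. The documents do not support that. The confirmed discrepancy understates what the table implies, the ramp gives about 98%, and the constant gap gives about 80%. If baseline is modelled as an outcome, both shapes exceed 90%. Lower values need random-slope variances that the protocol does not supply. Nor does 10.7 say that the blinded check will reuse this table or formula; it says only that the check will assess whether the projected size is adequate.

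**What to change.** Recompute 10.6 for the alpha_1 test of 10.3.1. State:
- the assumed difference at weeks 4, 8, 13 and 26;
- the covariance, including the random slope in 10.3.1, with a range where no data exist;
- how baseline enters, since 10.6 calls it a covariate and 10.3.1 models it through the intercept;
- the dropout pattern.

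Then restate the power at 200 per arm. Reconcile the 85% with the 165 row by going back to the source of the graph and the table, without presuming which is right. If the table is kept, name the contrast it was computed for. Name the attrition rate that the 80% statement is meant to cover; on the table's figures at rho 0.5 and 50% attrition, 200 per arm gives about 77% at effect 0.4 and about 81% at 0.42.

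The cost is rewriting one section. Enrolment does not change. The downside is that a stated power figure may become less favourable.

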10.7 Interim Analysis

In coordination with the Data and Statistics Center, a blinded interim variance check of the primary outcome measure will be conducted to assess the adequacy of the projected study sample size since this parameter is being estimated from limited data. The analysis will be conducted when approximately 200 participants (about 100 per arm) have been enrolled and have been assessed at the 3-month follow-up point. A subset of these participants for whom 6-months post-randomization data are available will be examined to determine the consistency in the variance of the primary endpoint across time.

A DSMB will monitor the trial's progress. No interim analyses other than the blinded variance check are proposed for the trial. An interim analysis could still be performed to assess efficacy, futility or safety if requested by the DSMB or NIDA. Trial monitoring guidelines for early stopping considerations of benefit are based on an O'Brien-Fleming boundary (O'Brien and Fleming, 1979) using a 2-sided 0.05-level upper boundary. The monitoring guidance for early stopping considerations for lack of benefit or for futility will be based upon an approach of conditional probability (Turnbull and Jennison, 2000). Additional safety interim looks will be performed (without formal testing being performed) as per the DSMB's request.

SIGNATURES					
SPONSOR'S REPRESENTATIVE					
Typed Name	Signature	Date			
CCTN Designee					

INVESTIGATOR (S)

- I agree to conduct this clinical study in accordance with the design and specific provisions of this protocol and will only make changes in the protocol after notifying the sponsor except when necessary to protect the safety, rights, or welfare of participants.
- I will ensure that the requirements relating to obtaining informed consent and institutional review board (IRB) review and approval in 45 CFR 46 are met.
- I agree to report to the sponsor adverse experiences that occur in the course of the investigation, and to provide annual reports and a final report in accordance with 45 CFR 46.
- I agree to maintain adequate and accurate records and to make those records available for inspection in accordance with 45 CFR 46.
